We will utilize a mixed-methods approach, drawing upon both qualitative and quantitative data from clinic site visits, clinic surveys, key informant interviews, follow-up calls, Medicaid administrative claims, and the OCHIN electronic health record (EHR).

Background and Significance:

The common practice of reimbursing primary care providers through a fee-for-service model hampers efforts to develop patient-centered medical homes: it rewards a high volume of face-to-face clinic visits, which does not necessarily lead to value, quality, and patient-centered care. This is especially problematic in Community Health Centers (CHCs), which are currently paid based on the Prospective Payment System (PPS) rate, a fee-for-service model. To reform this payment model in CHCs, Oregon developed an Alternative Payment Methodology (APM) that converts PPS (Medicaid revenue) to a prospective, capitated per-member per-month rate. The Oregon Primary Care Association (OPCA) is providing technical assistance to the APM clinics, with funding from the Robert Wood Johnson Foundation. The APM project seeks to (i) incentivize providing value over volume of visits, (ii) support comprehensive treatment modalities for patients with complex needs, and (iii) allow CHCs to focus more of their resources on population health initiatives.

APM is being implemented in several phases. Three CHC organizations are participating in Phase I of the APM demonstration project, which kicked off on March 1, 2013. Five additional CHC joined Phase II July 1, 2014 or October 1, 2014. Phase III began July 1, 2015 with three additional CHC organizations. Each CHC organization may include several clinics. All but one of the APM CHCs are members of the OCHIN community health information network practice-based research network, with a single, shared EHR. In this study, we propose to evaluate the APM clinics and/or patients matched to an equal number of control clinics and/or patients that are part of the OCHIN network.

Preliminary Studies / Progress Report:

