Econometric analyses. Using difference-in-differences methods, we will calculate the average pre-post APM difference in spending of patients in APM intervention clinics, subtracted by the average difference among patients in comparison clinics. Changes in spending after APM implementation in the intervention

clinics vs. spending changes in the control clinics will “net out” any secular changes not related to APM. Any remaining significant differences in outcome – the DID – are attributed to the APM intervention. These findings will help to assess whether the APM intervention can help reduce costs, and if so, whether the reduction comes from lower spending at the CHC level or through reductions in potentially unnecessary or inefficient use of specialty and hospital services. We note that CHCs are not financially at risk for services outside of the CHC and thus do not have incentives to act as gatekeepers to care. Thus, reductions in spending for specialty services and other external services would most likely reflect improvements in internal care delivery.

Analytically, the difference-in-differences estimate is represented by the marginal effect on the interaction between a dummy variable indicating that the observations occur in the post-APM period and a dummy variable indicating the individual’s attribution to an APM intervention clinic. We will also include patient-level variables to account for predisposing factors and need for services. A variety of issues must be addressed in our DID estimation:

Definition of external services. External services will be defined as any care occurring outside of the CHC, e.g., emergency department visits, hospitalizations, and other ambulatory care that takes place in settings other than the CHC.

Accounting for clinic-level effects. Our study will focus on the “treatment-effect” of the APM: how does the transition to a capitated payment system affect health care spending? Since this is our main focus, our approach may include use of clinic-level fixed effects to net out any time-invariant differences in clinic-level cost outcomes. However, recognizing the potential interest in clinic-level effects, in secondary analyses we will test hierarchical (mixed) models to more specifically model (i) clinic-level variation and (ii) patient-level variation.

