Modeling health care costs. As in many analyses of a patient’s health care costs, in any given year, many patients will have no visits or expenditures. Thus, our dependent variable will have a cluster of observations at zero. We will use a well-validated approach for modeling this phenomenon: the 2-part model.⁵³ Part 1 will use a logistic regression to estimate the probability of any expenditure. Part 2 will focus on individuals with non-zero expenditures. We will use recent literature to guide the appropriate estimation approach, taking into account the potentially skewed distribution of the dependent variable.^{54,55}

Accounting for all expenditures. Estimates of changes in spending must account for all expenditures, including capitated and fee-for-service (FFS) payments. Of note, Oregon’s Medicaid managed care organizations (MCOs) provide encounter data to the state Medicaid agencies in lieu of FFS claims, a common practice in many states. These data are assessed for general accuracy and consistency and have been used by states to set managed care payment rates. In order to attach “paid” amounts to these encounter claims, we will impute a “paid” amount across all FFS and MCO claims (that is, any external services for which there would be payment outside of the APM capitation rate) based on the median FFS payment. The study team has used this approach previously and has extensive experience in the data structures, elements, values, means of combining records and methods for aggregating and measuring service dimensions.^{25,56} In summary, creation of the expenditure variable will be based on a blend of actual FFS payments, recorded capitation rates, and, where necessary, imputed expenditures that have served as the actuarial basis for rate setting in Oregon.

Modeling interaction terms. In non-linear models (e.g., the 2-part model) the interpretation of the interaction effect cannot be directly calculated from the coefficient on the interaction term.⁵⁷ Our approach will be to estimate the 2-part model, save those coefficients, and use empirical simulation (also known as “recycled predictions”) methods to determine the APM’s average effect using bootstrapping to derive 95% confidence intervals.

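### The spending DID is attributed to the APM without stating parallel trends or planning any comparison of pre-APM trends

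*Combined protocol and SAP*

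**What the plan says.** The Econometric analyses section defines the spending effect as the average pre-post change in APM clinics minus that in comparison clinics. The control change is said to remove "any secular changes not related to APM", and the conclusion follows directly: "Any remaining significant differences in outcome – the DID – are attributed to the APM intervention".

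The estimate is the marginal effect on the interaction of "a dummy variable indicating that the observations occur in the post-APM period and a dummy variable indicating" attribution to an APM clinic. Two adjustments are named. One is firm: "We will also include patient-level variables to account for predisposing factors and need for services". The other is optional: "our approach may include use of clinic-level fixed effects to net out any time-invariant differences in clinic-level cost outcomes". For the two-part cost model, the subsection on interaction terms says: "Our approach will be to estimate the 2-part model, save those coefficients, and use empirical simulation".

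Start dates appear in Background and Significance, for APM organizations only. The first wave is described thus: "Three CHC organizations are participating in Phase I of the APM demonstration project, which kicked off on March 1, 2013". The second wave came more than a year later and had two possible dates: "Five additional CHC joined Phase II July 1, 2014 or October 1, 2014". Three more organizations followed in Phase III, from July 1, 2015. Quantitative data collection provides for at most three pre-APM years and at least three post-APM years. The Aims 1 and 2 Evaluation Summary adds a transition period of a length still to be determined.

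**The concern.** A DID identifies a treatment effect only if the two groups' outcomes would have moved in parallel without the treatment. The plan presents this as something the controls deliver, when it is an assumption. The only condition in the attribution sentence is statistical significance, which guards against chance and not against a drift that began before the APM.

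The section says that several issues must be addressed in the DID estimation and lists six: external services, clinic effects, cost modelling, completeness of expenditures, interaction terms and repeated observations. Parallel trends is not among them. No other section mentions leads, placebo periods or a comparison of pre-APM trends.

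Hypotheses 2a and 2b rest on this estimate. If spending in APM clinics was already falling relative to controls, the stated rule would report that decline as an APM saving. If it was rising, a real saving could be hidden.

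**Working it through.** The plan gives no effect size, spending mean, SD or trend, so there is no figure of its own to reproduce. The checks below show how a drift would enter the estimate.

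**1. Do the planned safeguards cover trends?**
- Matching (Aims 1 and 2 Evaluation Summary) and optional propensity scores (Statistical analyses, Patient-level) target observed imbalance. Matching on pre-APM spending trend is not mentioned.
- Clinic fixed effects are optional and remove only time-invariant differences.
- Baseline descriptives (Clinic-level) look at how baseline data differ, with no trend comparison stated.
- Analyses by phase and time of entry (Clinic-level) are optional and unspecified, and they sit outside the spending section.

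None of these states or checks equal trends.

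**2. Linear scale.** Let g be the residual APM-minus-control drift per year after matching and covariates (assumed), with no APM effect. The false DID is g times the distance between the period midpoints:

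false DID = g × (pre/2 + gap + post/2)/12, in months.

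| Pre | Gap | Post | False DID |
|---|---|---|---|
| 36 | 0 | 36 | (18 + 0 + 18)/12 = 3.0 × g |
| 36 | 6 | 36 | (18 + 6 + 18)/12 = 3.5 × g |
| 24 | 0 | 36 | (12 + 0 + 18)/12 = 2.5 × g |
| 12 | 0 | 36 | (6 + 0 + 18)/12 = 2.0 × g |
| 36 | 0 | 70 | (18 + 0 + 35)/12 = 4.4 × g |

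The last row is Phase I followed from March 1, 2013 to the end of the EHR window, December 31, 2018 (70 months).

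**3. Two-part scale.** The plan fixes a logistic first part and leaves the second open; a log link is assumed here. With flat controls, 36/36 months and proportional drift, the false effect is exp(3g) − 1. That is 1.51%, 3.05% and 6.18% of spending for g = 0.5%, 1% and 2% per year.

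These figures do not carry over when the probability of any spending is also changing in controls. Take common growth in that probability of 2% per year, g = 1% placed in that probability, 36/36 months, and probabilities set at the APM start date (all assumed). Without an APM effect, the model predicts for APM patients after the start

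expit[logit(APM pre) + logit(control post) − logit(control pre)].

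- APM 0.5, control 0.7: the period means are 0.4782 and 0.5232 (APM pre, post) and 0.6794 and 0.7214 (control pre, post). The prediction is 0.5282, so the false effect is 0.5232/0.5282 − 1 = −0.95%.
- APM 0.7, control 0.5: 5.32%; with g = 0 it is already 2.33%.
- Both 0.7: 2.85%.

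So whether trends are parallel depends on the scale, and the scale has to be named.

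**4. What pre-APM data exist?** From January 1, 2010 to the four start dates is 38, 54, 57 and 66 months, so three yearly pre-periods fit the EHR window in every phase. The Medicaid claims, which carry spending, have no stated dates and no stated minimum pre-APM span. With the last pre-APM year as reference, yearly periods give two leads from 36 months, one from 24 and none from 12.

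**5. Dating of controls (minor).** No rule says when the post-APM period starts for a control. A common linear trend cancels with equal windows whatever the dates. With 36/36 windows, a common step of size s occurring d months from the start date moves the pre-post difference by s × (1 − |d|/36). Two dates 28 months apart (March 1, 2013 and July 1, 2015) therefore differ by at most 28/36 = 0.78 × s. Identical dates differ by 0.

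**The case against.** The strongest reply is that the attribution does not stand alone. It follows matching, patient covariates and possibly clinic fixed effects; a same-patient cohort is planned for some comparisons; models are to be refined iteratively. That much is right, and a reader who inferred that the plan has no protection against confounding would go too far. What is missing is narrower: a stated identifying assumption and a check that bears on trends.

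A second reply is that three pre-APM years may not exist for claims, so yearly leads could be impossible. This stands. The plan promises only up to three years, and the remedy must adapt to what is available.

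A third is that leads may be too imprecise to help. This also stands in part. Eleven organizations joined (3 + 5 + 3), but Background and Significance says all but one are OCHIN members, which leaves about 10 with the linked EHR data. Imprecise leads are still worth showing, because they tell the reader how much drift cannot be excluded.

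A reader might also infer from the undated controls that the DID is seriously distorted. The documents do not support that. An equal-sized matched design points to the partner's date, and 0.78 × s needs both a control dated to the opposite extreme phase and a step at the worst moment. This is a clarification only.

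**Conclusion.** The concern holds as an unstated assumption and a missing check. Followed as written, the rule would report a pre-existing differential drift in spending as an APM effect, and nothing planned would reveal it. On a linear scale the error is 3.0 × g with 36/36 months, 2.0 to 2.5 × g with 12 to 24 pre-APM months, and more with a transition gap or longer follow-up. The simple percentages for the two-part model apply only when controls are flat.

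One might infer that trends did differ, or that the spending result will be wrong. The documents do not support either: g is purely an assumption, and good matching could make it small. The DID design can stand. Its causal wording should be made conditional and the check added before the spending analysis is run.

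**What to change.** 1. Add an event-study version of the spending DID over whatever pre-APM claims are available, with the last pre-APM period as reference. Use yearly leads if three pre-APM years exist, and half-yearly or quarterly leads if fewer. Report the leads as recycled-prediction contrasts on the spending scale, with confidence intervals, beside the DID. State that with about 10 OCHIN-member APM organizations they may be imprecise, and that they can support parallel trends but not prove them.
2. Replace the attribution sentence with wording such as: the DID is interpreted as an APM effect only under parallel trends on the stated scale, judged together with the reported leads.
3. Do the same for the Aim 1 DID (Statistical analyses, Clinic-level), on that model's own scale.
4. As a clarification, state that each matched control takes its APM partner's start date and transition period.

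The cost is a few sentences in the plan and modest extra programming. The main drawback is that the leads may have wide intervals and leave the question open.

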Oregon Health & Science University RESEARCH PROTOCOL

Protocol Title:

Evaluating Community Health Centers' Adoption of a New Global Capitation Payment (eCHANGE)

Principal Investigator:

[name]

Assistant Professor, Oregon Health & Science University Department of Family Medicine
[name]
[name]

[contact]

Sponsor:

Robert Wood Johnson Foundation, grant #71125
Agency for Healthcare Research and Quality (AHRQ)

Specific Aims:

Aim 1: Assess pre-post Alternative Payment Methodology (APM) changes in internal services utilization and quality of clinical care delivered in intervention sites, as compared with control sites.

Hypothesis 1a: Patterns of internal services utilization (e.g., face-to-face visits, e-mail visits) will change among intervention clinics' patients from pre- to post-APM, while control clinics' patients' rates will not change.

Hypothesis 1b: Intervention site patients will achieve greater pre-post improvements in quality of care delivered internally, as compared to the rates of improvement for patients in control clinics.

Aim 2: Measure pre-post changes in patients' utilization of external services (e.g., emergency department) and overall costs to the Medicaid program among patients from intervention clinics, as compared to patients from control clinics.

Hypothesis 2a: Expenditures attributed to external services will decrease for patients from intervention clinics, but these expenditures will remain the same or increase for patients in the control clinics.

Hypothesis 2b: Total Medicaid expenditures will decrease for patients from intervention clinics, while expenditures for patients from control clinics will remain the same or increase.

Aim 3: Study the change processes associated with APM implementation, including the organizational, workflow, and service delivery changes made in the Community Health Centers (CHCs) during and after APM implementation.

Hypothesis 3a: APM clinics will make fundamental pre-post changes in patterns of clinical care delivery and staff workflow.

Hypothesis 3b: There will be variability among the intervention clinics in what changes are successfully achieved, associated with vision, approach, strategic planning, and other clinic characteristics.

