Data included in the datasets Once the Medicaid-OCHIN EHR link is created, names, addresses, social security numbers and ID #s will be removed by the OCHIN analysts and a study ID will be given to the records that does not stem from any identifiers prior to sending the datasets to OHSU. OCHIN will maintain, but not share with OHSU the crosswalk that links the study ID to the identified data.

Inclusion criteria. OCHIN's EHR data includes internal services utilization and care quality on all patients seen, regardless of insurance type (Aim 1). We will assess the APM's impact on the entire clinic population (aged 2-64) as well as relevant subpopulations (e.g., Medicaid-insured, uninsured, APM patients). For some comparisons, the denominator will be patients with clinic contact. Patients in a clinic's panel will not necessarily be the same individuals in the pre- vs. post-APM period. Because APM might result in fewer face-to-face visits, we will work with our expert advisors to determine what "counts" as contact with the clinic. For some comparisons, we will create a longitudinal cohort of the same patients over time. Assessment of external services utilization and overall costs will focus on the Medicaid-insured (Aim 2).

Study variables. We adapted Aday and Andersen's model of health care utilization to help us understand the interplay between *predisposing factors, enabling / hindering factors, and need for care*, their impact

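### The plan says in advance that lower external spending most likely means better internal care, but specifies no spending analysis that could tell this apart from lost referrals

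*Combined protocol and SAP*

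**What the plan says.** Hypothesis 2a (Specific Aims) predicts: "Expenditures attributed to external services will decrease for patients from intervention clinics". The outcome is a single total. Under Econometric analyses, the paragraph on the definition of external services sets its scope: "External services will be defined as any care occurring outside of the CHC, e.g., emergency department visits, hospitalizations, and other ambulatory care".

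The opening of Econometric analyses then takes two interpretive steps. The first is causal: "Any remaining significant differences in outcome – the DID – are attributed to the APM intervention". The second concerns meaning: "reductions in spending for specialty services and other external services would most likely reflect improvements in internal care delivery". The reason given for the second step is that "CHCs are not financially at risk for services outside of the CHC and thus do not have incentives to act as gatekeepers to care".

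The same section wants to know whether any saving arises inside the CHC or from avoidable or wasteful specialty and hospital use. It does not define such use, and it takes specialty and hospital services together.

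The quantitative Inclusion criteria paragraph contains a relevant remark, "Because APM might result in fewer face-to-face visits", but uses it only to introduce the question of what should qualify as contact with the clinic.

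**The concern.** The premise is narrower than the conclusion. Absence of a gatekeeping incentive means that a CHC gains nothing by holding patients back from outside care. It says nothing about passive loss. If patients are seen less often, some referrals may not be made and some problems may not be detected. Specialty and other ambulatory spending would then fall without any improvement in care.

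A DID on total external spending gives the same sign in either case. Netting out secular change supports attribution to the APM, but does not show by which route the APM acted. Under Importance of the Knowledge to be Gained, the protocol says the results are meant to inform the spread of alternative payment to other CHCs and primary care settings. For that use, whether a saving came from better care or from care not received matters as much as the saving itself.

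**Working it through.** The plan states no figure on this point, so there is nothing to reproduce. The check has two parts.

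**What the plan specifies that could separate the two explanations**

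- *Spending by setting.* Emergency, hospital and other ambulatory care are named as examples in the definition, but no model is specified for each. The only stated split is CHC spending against specialty and hospital spending together.
- *External utilization.* It is an Aim 2 outcome and a primary dependent variable under Study variables. The final measures are still to be chosen with the advisory group, and no referral or specialty-access measure is named.
- *Quality.* Hypothesis 1b compares pre-post improvement between intervention and control sites, but only for care delivered internally.
- *Recommended services.* A count of those received is analysed, as an exploratory secondary analysis (Statistical analyses, Patient-level).
- *Joint reading.* Nothing requires any of these results to be considered before a fall in spending is interpreted.

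**Illustration with assumed inputs**

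The documents give no spending mix, so all three inputs are assumptions:

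- s = share of external spending that is specialty or other ambulatory care: 20%, 35%, 50%
- f = fall in that component through lost referrals: 10%, 20%, 30%
- g = change in emergency plus hospital spending: 0% or +5%

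Change in total external spending = −s·f + (1 − s)·g.

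The fall in emergency and hospital spending alone that gives the same total as the g = 0 case is s·f / (1 − s).

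| s | f | Total, g = 0 | Total, g = +5% | Equivalent emergency/hospital fall |
|---|---|---|---|---|
| 20% | 10% | −2.0% | +2.0% | 2.5% |
| 20% | 20% | −4.0% | 0.0% | 5.0% |
| 20% | 30% | −6.0% | −2.0% | 7.5% |
| 35% | 10% | −3.5% | −0.25% | 5.4% |
| 35% | 20% | −7.0% | −3.75% | 10.8% |
| 35% | 30% | −10.5% | −7.25% | 16.2% |
| 50% | 10% | −5.0% | −2.5% | 10.0% |
| 50% | 20% | −10.0% | −7.5% | 20.0% |
| 50% | 30% | −15.0% | −12.5% | 30.0% |

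Worked row (s = 35%, f = 20%): −0.35 × 20% = −7.0%. With g = +5%, −7.0% + 0.65 × 5% = −3.75%. The equivalent fall is 7.0% / 0.65 = 10.8%.

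Two things follow. A total fall of 2% to 15% is compatible either with lost specialty care alone or with a 2.5% to 30% fall in emergency and hospital spending alone. And when emergency and hospital spending rises by 5%, the total is still zero or negative in 8 of the 9 combinations, so a rise in acute spending could be hidden within an apparent saving. The table shows that the aggregate cannot identify the mechanism. It says nothing about how likely either mechanism is.

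**The case against.** Much can be said for the plan, and most of it stands.

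- A reader might infer a decision rule that credits every fall in external spending to better care. The text does not support that. The sentence is worded as a likelihood, sits in a rationale paragraph, and sets no threshold or reporting criterion. The estimator and the Hypothesis 2a contrast do not depend on it.
- A reader might infer that only a pooled total will be analysed. The plan does not say so. It names the settings, includes external utilization as an outcome, and excludes no component analysis. The gap is one of prespecification.
- A reader might infer that the plan expects visits to fall and referrals with them. It says only that face-to-face visits might fall. Hypothesis 1a also counts e-mail visits, so contact may change form rather than shrink. No section describes an under-referral pathway; it is a plausible alternative that the stated premise leaves open.
- The quality comparison, the recommended-services analysis and the Aim 3 study of service delivery could each reveal under-provision. They are partial safeguards: none is specified as a measure of specialty referral, and none is tied to the spending result.

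What the objection does not answer is the inference itself. Lack of a gatekeeping incentive does not make better internal care the most likely explanation of lower external spending.

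**Conclusion.** The concern holds in a limited form. The plan states a favourable reading of lower external spending in advance, on a premise that does not exclude passive under-referral or under-detection, and prespecifies no spending contrast that would help tell the explanations apart. As written, it cannot answer its own question about avoidable external use. A fall driven only by lost specialty care could be read as improved care. A reader might go further and conclude that it would be reported as a success, but the documents do not support that, because the wording is hedged and other planned results might contradict it.

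The size is unknown. The 2–15% range rests entirely on the assumed shares and falls above. The validity of the aggregate DID as an estimate of the change in spending is not in question here; the point concerns its interpretation and the components reported beside it. It should be corrected before the spending results are seen.

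**What to change.** 1. Delete the sentence quoted above from Econometric analyses, or make it neutral: lower external spending may reflect better internal care, reduced referral or detection, or both.
2. Keep the aggregate Hypothesis 2a DID and prespecify the same analysis separately for emergency, inpatient, and specialty/other ambulatory spending. The planned two-part model with bootstrap intervals can be used for each. Because the model is non-linear, separately fitted components need not sum exactly to the aggregate, and the report should say so.
3. State that a fall in external spending will be interpreted jointly with these components and the Aim 1 quality DID, and that a fall confined to specialty/other ambulatory care is not by itself evidence of improved internal care.

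A stricter rule, crediting the APM only if emergency or hospital spending falls, is not recommended. It would deny credit where CHCs appropriately take on work previously sent out, and would replace one presumption with another.

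The cost is a few lines of analysis-plan text, classification of the planned Medicaid claims by setting, and a little more analysis. Component estimates will be less precise than the aggregate, so a component interval that includes zero should not be read as showing no change. No new data collection is needed.

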total Medicaid spending.	(We will assess how long implementation takes and include it as transition time to our analyses)	OCHIN EHR data; Medicaid administrative data (including intervention CHCs' per-member per-month capitated payment rates)	Population: Medicaid-enrolled patients at intervention and control clinics aged 2-64	of healthcare spending. Matching methods will be utilized to reduce the observed bias and to adjust for imbalances between intervention and control clinics and/or patients.
--------------------------	--	--	--	--

Data Sources

EHR data. We will assemble a dataset of EHR data elements including all demographics, healthcare utilization, diagnoses, treatment, and health insurance coverage start and stop dates for all established patients age 2-64 for patients of APM clinics and their matched controls. We will include data from the following dates: no earlier than January 1, 2010 – December 31, 2018. The EHR is **centrally hosted and managed** at OCHIN and shared across all study CHC clinics. OCHIN maintains this central data warehouse, and the data are standardized across all OCHIN CHCs and regularly checked for accuracy.

Medicaid administrative data. These data will provide information on external services received and costs incurred. Oregon's Medicaid recipients are assigned unique individual identification (ID) numbers, facilitating data linkages across multiple databases, including the OCHIN EHR data. We will use claims and cost data from Medicaid.

Linkage between EHR and Medicaid administrative data. Project staff will use state ID numbers to create individual-level linkages between OCHIN EHR and Medicaid data.³⁷⁻³⁹ **All transfers will be done securely.** A de-identified dataset will be transferred to OHSU. The lead research analyst at OHSU has obtained security clearances to work with OCHIN's data team to assist with preparing the dataset to transfer to OHSU.

This study is being conducted in collaboration with OCHIN. The State of Oregon data will be shared with OCHIN under a Data Access Agreement. OCHIN will then share Medicaid and OCHIN EHR data with OHSU under a Data Use Agreement.

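### The two-part spending model has no term for Medicaid-enrolled time, so any differential change in enrolled months would be read as an APM effect on spending

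*Combined protocol and SAP*

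**What the plan says.** All references are to the combined protocol and SAP.

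- **Econometric analyses.** The estimand is stated as: "we will calculate the average pre-post APM difference in spending of patients in APM intervention clinics", minus the corresponding change in comparison clinics. On covariates: "We will also include patient-level variables to account for predisposing factors and need for services". Significant differences that remain "are attributed to the APM intervention".
- **Modeling health care costs.** The two-part model is motivated by the observation that "in any given year, many patients will have no visits or expenditures". Then: "Part 1 will use a logistic regression to estimate the probability of any expenditure" and "Part 2 will focus on individuals with non-zero expenditures".
- **Aims 1 and 2 Evaluation Summary (table).** The Medicaid population is "Medicaid-enrolled patients at intervention and control clinics aged 2-64", with no minimum or continuous enrollment.
- **Inclusion criteria.** Panel members may differ between the two periods. A cohort of the same patients is foreseen for some comparisons only.
- **EHR data.** The extract includes "health insurance coverage start and stop dates for all established patients age 2-64". No use of these dates in the spending model is stated.

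The econometric section lists the issues its DID has to handle: external services, clinic effects, zeros, completeness of expenditures, interaction terms and repeated observations. Enrolled time is not among them.

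**The concern.** A patient covered for part of a period has less opportunity to generate a claim, and a smaller total, than one covered throughout, whatever the payment model does. Spending per patient is therefore the product of enrolled time and spending per unit of time. The DID as specified does not separate them.

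H2a and H2b both predict a fall in spending at intervention clinics. If control patients' enrollment lengthens more, the DID shows a saving that did not occur. If intervention patients' enrollment lengthens more, a real saving is masked. In both cases the plan's interpretation rule assigns the result to the APM. The capitated component is paid per member per month, so that part of total spending scales directly with months enrolled.

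**Working it through.** The plan gives no spending level, enrollment length or power calculation for this analysis, so there is no figure to reproduce. All numerical inputs below are assumptions.

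**1. Closed form.** Let spending be *c* per member-month in both arms and periods, with no APM effect, and let *m* be mean months enrolled.

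DID = *c* × [(change in *m*, intervention) − (change in *m*, control)]

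Relative to pre-period spending *c* × *m*₀, this is (differential change in months) / *m*₀. The dollar rate cancels. With *m*₀ = 9:

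- 0.5 month: 0.5/9 = 5.6%
- 1 month: 1/9 = 11.1%
- 2 months: 2/9 = 22.2%

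The sign is negative if control enrollment rises more and positive if intervention enrollment rises more. At $400 per member-month, one extra intervention month gives $400 on 9 × $400 = $3,600. For *m*₀ between 6 and 11, half a month gives 0.5/6 = 8.3% down to 0.5/11 = 4.5%, and one month gives 1/6 = 16.7% down to 1/11 = 9.1%.

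An equal change of *d* months in both arms cancels when *c* is the same in both. If monthly spending differs between arms, *d* × (*c* intervention − *c* control) remains.

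**2. Simulated two-part model.** Logit plus log-link gamma with recycled predictions; 40,000 persons per cell; one run per scenario; $300 per member-month; 0.12 claim episodes per month; mean 9 baseline months, kept between 3 and 12; about one third with zero spending; true APM effect zero. Entries in the last three columns are DIDs as a percentage of baseline.

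| Months added (APM, control) | Realized differential (months) | No months term | Months in both parts | Per member-month |
|---|---|---|---|---|
| 0, 0 | −0.01 | −2.7% | −2.7% | −2.6% |
| 1, 1 | 0.02 | −0.8% | −0.8% | −0.9% |
| 0, 0.5 | −0.46 | −6.1% | −0.9% | −0.9% |
| 0, 1 | −0.87 | −8.3% | +1.6% | +1.5% |
| 0, 2 | −1.69 | −18.3% | +0.8% | +0.6% |
| 1, 0 | +0.92 | +10.9% | +0.2% | +0.5% |

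The first two rows show the simulation noise. Within it, the third column follows the closed form and the last two columns stay near zero. Months entered this check as categories.

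**3. Part 1 and the offset.** With an assumed 0.15 claims per month, P(any) = 1 − exp(−0.15 × months):

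- 9 months: 1 − exp(−1.35) = 74%, odds 2.857
- 10 months: 1 − exp(−1.50) = 78%, odds 3.482

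The log odds ratio is ln(3.482/2.857) = 0.198. An offset of log months in a logit removes ln(10/9) = 0.105, and 0.105/0.198 = 53%. Almost half of the artefact would stay, so the coefficient must be free.

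**4. Part 2.** Under the same assumptions, mean spending per month among spenders is *c*/P(any): *c*/0.741 = 1.350*c* at 9 months and *c*/0.777 = 1.287*c* at 10. The ratio is 0.953. Dividing by months therefore leaves a dependence on months of about −4.6% in Part 2 taken alone, because selection into Part 2 also depends on months. It is offset only if Part 1 is evaluated at each group's own months. If predictions hold months fixed, Part 2 needs the months term too.

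**The case against.** The strongest reply is that the plan is silent rather than wrong. The yearly unit appears only in the rationale for the two-part model, and the paragraph on repeated observations speaks of pre- and post-APM periods. No covariate list is declared closed; the patient-level section allows time-dependent covariates, propensity methods and iterative refinement. Both arms are Oregon Medicaid patients in one network with matched controls, so statewide coverage changes may largely cancel. H2b concerns total expenditure: if the APM alters how long patients stay enrolled, that is part of its cost to Medicaid, and adjustment would remove it. Finally, the coverage dates are listed under EHR data, and no Medicaid eligibility file is named.

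Much of this limits the point. A reader might infer that the plan fixes annual spending as the outcome and rules out an enrollment term; the text does neither. A reader might also infer that bias is expected; no enrollment lengths are given and no divergence is shown. The estimand and data-quality remarks stand and shape the fix.

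The gap itself remains. The spending section names its covariates and its issues, and enrolled time is in neither. Using whole periods instead of years does not equalize months. Baseline matching does not remove a divergence that arises later, and a same-patient cohort need not have equal months.

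**Conclusion.** The point holds as a conditional one. As specified, the two-part DID cannot distinguish a change in spending per enrolled month from a differential change in months enrolled, and it assigns both to the APM. With constant and equal monthly spending and 9 baseline months (assumed), the relative bias is about 5.6% for a half-month differential and 11.1% for one month. Its actual size and direction cannot be determined from the documents.

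The false-zero problem in Part 1 should not be extended equally to both hypotheses. Capitation payments enter total spending, so an enrolled APM patient after implementation has non-zero total spending even without a visit. The 74% to 78% shift is therefore mainly relevant to external spending under H2a. For H2b in that group, the problem lies in the amount.

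**What to change.** State the following in the econometric section:

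1. Derive Medicaid-enrolled months per patient and period from the coverage dates, and check them against Medicaid administrative data where possible.
2. Include log enrolled months in the Part 1 logit as a covariate with a free coefficient, and check its functional form. Use log months as an offset only in log-link count models, such as those for external utilization.
3. Model Part 2 as spending per enrolled month, weighted by months, and keep log months as a covariate there when recycled predictions hold months fixed.
4. Report H2a and H2b as a DID in dollars per member per month.
5. As companion results, report the DID in enrolled months and the per-patient total DID, so that an APM effect on enrollment length is shown rather than adjusted away.

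The cost is one derived variable, some added analysis and a second estimand to report beside the per-patient total. No new data collection is needed if the EHR coverage dates prove accurate enough for Medicaid months. That is not established in the documents and is the reason for the check in step 1.
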